#### **CR(2):**

$$\text{Exposure Duration (days)} = \text{Last Visit date} - \text{Baseline date} + 14$$

$$\text{Cumulative Difference (days)} = \sum_i \text{ABS}(\text{AD}_i - \text{SD}_i), \quad \text{where } i = \text{Week 0, 2, 4, 6, } \dots, \text{XX}$$

where  $\text{AD}_i = \text{Actual day of administration, for Week } i=0 \text{ to XX by 2}$   
 $\text{SD}_i = \{0, \quad \text{for Week } i=0\}$

$$\{14 + AD_{i-2}, \quad \text{for Week } i=2 \text{ to XX by 2 } \}$$

Note: XX represents the last completed visit in which study drug should have been administered. If subject is still in the study but  $AD_i$  is missing, then  $ABS(AD_i - SD_i) = 14$  for the missed Visit i.

**Table 12.1: Example**

Week	Scheduled day (1)	Scheduled day (2)	Actual day	ABS Diff (1)	ABS Diff (2)
0	0	0	0	0	0
2	14	14	13	1	1
4	28	27	29	1	2
6	42	43	-	14	14
8	56	57	55	1	2
10	70	69	69	1	0
Total	-	-	-	18	19
CR				66/84 = 0.79	65/84 = 0.77

Note that this example is for a 12 week study.

In case the actual day of administration is missing, the maximum deviation to the scheduled visit date will be assumed (ie 14 days). If for a scheduled visit date with 2 planned injections, the syringes were administered on 2 different days, the maximum day difference of the 2 actual dates to the scheduled visit date will be utilized.

For the measurement of treatment compliance in Part A, the exposure duration in Part A, identified as “Exposure Duration [a]”, will use the last of the open label injection visit dates:

- Exposure Duration [a] (days) = week 46 Visit/last injection date – Baseline date + 14

The cumulative difference will be calculated for all visits from Week 0 (Baseline) to week 46.

For the measurement of treatment compliance in Part B, the exposure duration in Part B, identified as “Exposure Duration [b]”, will use the last of the double-blind injection visit dates:

- Exposure Duration [b] (days) = week 94 Visit/last injection date – Week 48 injection/Week 48 Visit date + 14

The cumulative difference will be calculated for all visits from Week 48 to week 94.

For the measurement of treatment compliance in Part B post-flare, the post-flare exposure duration, identified as “Exposure Duration [f]”, will use the last of the injection escape Visit dates:

- Exposure Duration [f] (days) = last escape visit/last injection date – first Escape Week 0 injection /Escape Week 0 Visit date + 14

The cumulative Difference will be calculated for all visits from Escape Week 0 to last Escape visit.

## 12.3 SAP Amendment 1

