#### **2.3.3 Escape treatment**

Subjects experiencing a flare in Part B will be invited for an on-site visit to receive the next planned dose of investigational product (escape treatment). This visit will take place 2 weeks after the last assessment that resulted in meeting the flare criteria; or, at the discretion of the Investigator, at an earlier time point. As the start of escape treatment may vary from subject to subject, it will be referred to as “Escape Week 0”. Subjects will remain on the escape treatment for at least 12 weeks or until Week 96 of the regular visit schedule as described in Table 5.1 in the protocol, whichever is longer.

The assessment-schedule for subjects experiencing a flare in Part B will start 2 weeks after the flare condition is fulfilled; or, at the discretion of the Investigator, at an earlier time point and will end 2 weeks before Week 96 after Baseline of the regular assessment schedule. If the flare occurs late in Part B (at or after Week 82), the subject must receive the escape treatment for 12 weeks (eg, starting at Week 84 until Week 96). The final assessments at study end (as laid down for Week 96) must be performed 2 weeks after the last study dose administration accordingly.

Subjects receiving PBO or half-dose CZP (200mg Q4W) who experience a flare during the Double-Blind Period will escape to full-dose treatment (CZP 200mg Q2W) until the end of that period or for at least 12 weeks, whichever is longer. The escapers need to come back to the site at the time point of the escape (Week 0), 2 and 4 weeks after escape (Weeks 2 and 4), and every 12 weeks thereafter until the originally scheduled Week 96.

Subjects escaping from PBO to full-dose CZP (200mg Q2W) will receive a loading dose of CZP (400mg Q2W) at the 3 consecutive visits after the flare. Subjects escaping from half-dose CZP to full-dose CZP will receive CZP 200mg Q2W at the 3 consecutive visits after the flare. In order to maintain the blind, subjects escaping from half-dose CZP to full-dose CZP will receive a PBO-administration and a CZP 200mg administration at these 3 visits.

Subjects randomized to the CZP full-dose (200mg Q2W) treatment during the Double-Blind Period who qualify for escape will remain on their current treatment allocation. As with subjects escaping from half-dose CZP to full-dose CZP, these subjects will receive a PBO and CZP 200mg injection at the 3 visits after the flare in order to maintain the blind to the randomized treatment.

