## 7 MEASUREMENTS OF TREATMENT COMPLIANCE

Treatment compliance will be calculated for Part A, Part B and Part B post-flare separately. Part B summaries will not consider any post-flare escape treatment injection. There will be 2 approaches to calculate treatment compliance. The first will utilize the number of administered syringes and compare them to the scheduled expected number of injections. The sum of the difference in number of syringes between the actual used and expected syringes will be summarized. In addition, a ratio of compliance will be further computed based on the number of actual and expected syringes. The ratio of compliance will be summarized as a continuous variable and categorically ( $<0.80$ ,  $\geq 0.80$ – $\leq 1.0$  and  $>1.0$ ). The general formula for the compliance ratio (CR) is given as follows:

$$CR = \# \text{ actual syringes} / \# \text{ expected syringes}$$

The second approach defines compliance with study drug administration based upon comparing the actual day of administration with the expected day of administration. The expected day of administration will be based upon (1) the Baseline date and (2) the previous injection date. The

sum of the absolute difference in days between the actual and expected days will be summarized. In addition, a ratio of compliance will be computed based upon the actual and expected days for each of the 2 methods. The ratio of compliance will be summarized as a continuous variable and categorically ( $<0.80$ ,  $\geq 0.80$ ). The general formula for the compliance ratio is given as follows:

$$\text{Compliance Ratio (CR)} = \{[\text{Exposure Duration (days)}] - [\text{Cumulative Difference (days)}]\} / [\text{Exposure Duration (days)}]$$

The CR ranges between 0 and 1. Specific details are provided in Section 12.2.

Compliance based on these methods will be summarized by axSpA subpopulation and overall in Part A using the SS, by treatment group in Part B using the SSB and by treatment group in Part B Post-flare using the ETS. The compliance for Part B will be calculated based on the first injection in Part B and the compliance for Part B post-flare will be calculated based on the first injection in Escape Part.

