### **12.2 Compliance ratio calculation**

The general formula for treatment compliance is given as follows:

$$\text{Compliance Ratio (CR)} = \{[\text{Exposure Duration (days)}] - [\text{Cumulative Difference (days)}]\} / \{\text{Exposure Duration (days)}\}$$

There are 2 methods to determine the CR. CR(1) is based upon scheduled days which reference the Baseline Visits. CR(2) is based upon scheduled days which reference the previous dosing administration date. CR(1) and CR(2) each will be computed separately. The definition of exposure duration and cumulative difference varies for the 2 calculations. In all cases, if the subject was randomized, but study drug was never administered then the CR is equal to 0. The CR is limited to a range of 0 to 1. Therefore, if for any reason a negative value is computed, the CR must be set to 0. Specific details for each calculation follow.

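### SAP Section 12.2 does not say where the Part B day-based compliance sum ends for subjects who escape; read literally, it scores on-time subjects who escape at Week 86 or earlier below 0.80

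*SAP*

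**What the plan says.** SAP Section 7 calculates compliance separately for Part A, Part B and Part B post-flare, and tabulates Part B by treatment group. It adds that "Part B summaries will not consider any post-flare escape treatment injection". On reporting it says "The ratio of compliance will be summarized as a continuous variable and categorically"; for the day-based ratio the categories are below 0.80 and 0.80 or above.

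Section 12.2 defines CR as exposure duration minus cumulative difference, divided by exposure duration, with this floor: "if for any reason a negative value is computed, the CR must be set to 0". Four statements fix the Part B version:

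- **Range of the sum:** "The cumulative difference will be calculated for all visits from Week 48 to week 94".
- **Penalty:** "In case the actual day of administration is missing, the maximum deviation to the scheduled visit date will be assumed (ie 14 days"). The notes to CR(1) and CR(2) apply the 14 days while the subject is still in the study.
- **Denominator:** Exposure Duration [b] "will use the last of the double-blind injection visit dates". Its formula offers the Week 94 visit or the last injection date as the end point.
- **General upper limit:** "XX represents the last completed visit in which study drug should have been administered". The same note stands under CR(1).

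Section 2.3.3 keeps escapers in the study: "Subjects will remain on the escape treatment for at least 12 weeks or until Week 96", whichever is longer.

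**The concern.** An escaper is still in the study but, under Section 7, has no countable Part B injection from escape onward. If the sum runs to Week 94, every later double-blind visit scores 14 days. If the denominator stops at the last double-blind injection, numerator and denominator also cover different periods. The ratio then reflects when the subject escaped, not whether doses were taken on time.

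Escape follows flare, and flare is the primary outcome. A compliance table by arm built this way would show lower compliance wherever flares are more common, with no difference in dosing behaviour. Two programmers could also give the same subject 0 and 1.00, each with support in the text.

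**Working it through.** **The plan's own example.** In Table 12.1 the absolute differences sum to 18 and 19 days, with one missed injection scored 14. Exposure is 70 + 14 = 84 days. CR(1) = (84 − 18)/84 = 66/84 = 0.79 and CR(2) = (84 − 19)/84 = 65/84 = 0.77. Both match the SAP, so the formula is understood as intended.

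**Inputs for Part B.** Visits from Week 48 to Week 94 every two weeks number 24, or 24 × 14 = 336 days (the formula steps by two weeks for all arms). Take a subject dosed exactly on each scheduled day until escape at Week w. Then k = (w − 48)/2 double-blind injections were given and 24 − k visits remain. CR(1) and CR(2) coincide for this subject.

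**Three readings.**

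- (a) Sum to Week 94, exposure to the last double-blind injection: exposure 14k, penalty 14(24 − k), so CR = (2k − 24)/k, floored at 0.
- (b) Sum to Week 94, exposure to the Week 94 visit: CR = (336 − 14(24 − k))/336 = k/24.
- (c) General limit read as stopping at escape: no penalty, so CR = 1.00.

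| Escape week | k | Penalty (days) | Exposure in (a) (days) | CR (a) | CR (b) | CR (c) |
|---|---|---|---|---|---|---|
| 60 | 6 | 252 | 84 | 0 | 0.25 | 1.00 |
| 72 | 12 | 168 | 168 | 0 | 0.50 | 1.00 |
| 80 | 16 | 112 | 224 | 0.50 | 0.67 | 1.00 |
| 84 | 18 | 84 | 252 | 0.67 | 0.75 | 1.00 |
| 86 | 19 | 70 | 266 | 0.74 | 0.79 | 1.00 |
| 88 | 20 | 56 | 280 | 0.80 | 0.83 | 1.00 |
| 94 | 23 | 14 | 322 | 0.96 | 0.96 | 1.00 |

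Readings (a) and (b) put the 0.80 boundary in the same place: escape at Week 86 or earlier falls below it, and escape at Week 88 or later does not. Under (a), any escape up to Week 72 gives 0.

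**Size by arm.** Section 2.4 assumes flare-free proportions of 80/75/45% (Q2W/Q4W/placebo), so flare rates of 20/25/55%. With 70 subjects per arm that is 14, 17.5 and 38.5 flares, and placebo has 38.5/70 = 55% of them. For illustration, suppose that every flare leads to escape two weeks later and that flares are spread evenly over the 12 four-weekly visits from Week 52 to Week 96. Flares at the nine visits from Week 52 to Week 84 then lead to escape by Week 86. The share below 0.80 is 9/12 of the flare rate: 0.75 × 20 = 15%, 0.75 × 25 = 19% and 0.75 × 55 = 41%. With a constant hazard instead, the shares are 1 − 0.80^0.75 = 15%, 1 − 0.75^0.75 = 19% and 1 − 0.45^0.75 = 45%.

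**The case against.** The best defence is that the general limit already settles the matter. After escape no further double-blind injection is due, the subject follows a separate escape visit schedule, and a visit that no longer applies is not a missed visit. The Part A sentence in Section 12.2 is worded in the same way (Week 0 to Week 46). Both sentences may only name which visits belong to each period, leaving the general formula to fix where an individual's sum ends. Post-flare compliance has its own exposure duration and visit range, and Section 3.1 keeps post-flare assessments out of the Part B summaries. On that reading every on-time escaper scores 1.00.

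This reading is tenable, so the SAP does not make misclassification certain. It does not remove the conflict, for three reasons. Escape doses are also study drug, so an escaper keeps completing visits at which study drug is due, and the general limit does not clearly stop at escape. The sentence specific to Part B names a fixed Week 94, whereas Exposure Duration [b] and the post-flare sum have variable ends. The Part A parallel does not help escapers, because the still-in-the-study condition protects subjects who withdraw but not those who stay on escape treatment. By contrast, Section 10.1.2.1 cuts Part B exposure expressly at the start of escape treatment; Section 12.2 has no such words.

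A reader might also infer that the syringe-count ratio is wrong. The documents do not show this: Section 7 refers only to the scheduled expected number of injections and does not say how that number is set for escapers.

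**Conclusion.** Section 12.2 is internally inconsistent for escapers. The same perfectly dosed subject can receive 0, 0.50 or 1.00 for escape at Week 72, depending on which sentence the programmer follows. On the literal readings, escape at Week 86 or earlier falls below 0.80.

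A reader might infer that all escapers will be classed as non-compliant. The SAP does not support that: escape at Week 88 or later stays at 0.80 or above even on the literal readings, the general limit allows 1.00, and the SAP uses numerical categories without that label.

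The 15/19/41% figures are upper-end illustrations. They rest on the planning flare rates, an assumed timing (a constant hazard moves placebo to 45%) and every flare leading to escape. Section 3.2.22 also counts premature withdrawals and repeated missing scores as flares, and some of those subjects may never escape, so the true shares cannot be read from the SAP.

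Nor does it follow that efficacy conclusions are affected. The ratio feeds a descriptive by-arm table. The SAP uses it in no efficacy analysis and states no CR cut-off for the Per Protocol Set. The notional missed doses all fall after escape, so they could not explain the flares; the risk is that a table without this context is read that way. The point merits correction because the artefact differs by arm and the repair is simple.

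**What to change.** State in Section 12.2 that, for subjects who escape, both the Part B cumulative difference and Exposure Duration [b] cover only double-blind injection visits scheduled before the first escape injection, or before the Escape Week 0 visit date if none was given. Count later visits only in the post-flare ratio. An on-time escaper then has a CR of 1.00 at every escape week from 50 to 94, and a genuinely late or missed double-blind dose still lowers the ratio. For consistency, confirm that the expected syringe count in Section 7 uses the same window.

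The cost is one sentence in Section 12.2 and one filter in the compliance program. No clinical rule, endpoint or efficacy analysis changes.

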### Rationale for the amendment

The main purpose of this amendment is to implement the updates of Protocol Amendment 2 where the current assay for measuring ADA in plasma was replaced by a new method in order to align with current regulatory guidelines.

In line with the Protocol of the study, the Safety Set changed to include the subjects in open-label Part A as well. The previous defined Safety Set was changed to Safety Set Part B (SSB).

There is also the possibility to report one unscheduled ASDAS between two scheduled ASDAS assessments, the censoring time point changed and additional instruction for analysis are added.

Moreover, scores which should present an improvement (ASDAS-CII, ASDAS-MI, ASAS20, ASAS40, ASAS5/6, SF-36 PCS response and SF-36 MCS response) are not analyzed using Part B Baseline as reference.

A modified version of ASDAS-MI was added as sensitivity analysis for ASDAS-MI.

Analyses for time since diagnosis of disease and symptom duration were added to medical history.

### Modifications and changes

#### Global changes

The following changes were made throughout the SAP:

- In the summary tables for Part A, the axSpA subpopulation is used instead of mNY classification, since the data is presented for AS and nr-axSPA in the corresponding outputs. The term mNY classification is kept when it is presented or used as stratification factor.
- In safety outputs for Part A, SS is used instead of OLS and in safety outputs for Part B SSB is used instead of SS.
- Censoring point changed from week 92 to week 94.
- Analyses for ASDAS-CII, ASDAS-MI, ASAS20, ASAS40, ASAS5/6, SF-36 PCS response and SF-36 MCS response referring to Part B Baseline are removed.

#### Specific changes

In addition to the global changes, the following specific changes have been made (formats as missing spaces or redundant spaces are not listed):

#### Change #1

List of abbreviation

The following abbreviations were added:

Nab Neutralizing antibody

SSB Safety Set Part B

ADAb anti-CZP antibody

## Change #2

### 1 Introduction

The following protocol version was added:

- Protocol Amendment 2 dated 24 Jan 2018
- Protocol Amendment 2.1 (Taiwan) dated 27 Feb 18
- Protocol Amendment 2.2 (UK) dated 27 Feb 18

## Change #3

### 2.2.1.3.2 Other efficacy variables for subjects entering Part B

- ASDAS clinical improvement (ASDAS-CII, ASDAS-MI) using Part A Baseline and Part B Baseline as a reference
- ASAS20, ASAS40, ASAS5/6, and ASAS PR response using Part A Baseline Baseline and Part B Baseline as a reference
- BASDAI50 response using Part A Baseline and Part B Baseline as a reference
- SF-36 PCS response and SF-36 response using Part A Baseline and Part B Baseline as a reference

### Has been changed to:

- ASDAS clinical improvement (ASDAS-CII, ASDAS-MI) using Part A Baseline as a reference
- ASAS20, ASAS40, ASAS5/6, and ASAS PR response using Part A Baseline as a reference
- BASDAI50 response using Part A Baseline as a reference
- SF-36 PCS response and SF-36 MCS response using Part A Baseline as a reference

## Change #4

### 2.2.1.3.3 Other efficacy variables for subjects who experience a flare in Part B

- ASDAS clinical improvement (ASDAS-CII, ASDAS-MI) using Part B Baseline and Flare Baseline as reference
- ASAS20, ASAS40, ASAS5/6, and ASAS PR response using Part B Baseline and Flare Baseline as reference
- BASDAI50 response using Part B Baseline and Flare Baseline as reference
- SF-36 PCS response and SF-36 response using Part B Baseline and Flare Baseline as a reference

### Has been changed to:

- ASDAS clinical improvement (ASDAS-CII, ASDAS-MI) using Flare Baseline as reference
- ASAS20, ASAS40, ASAS5/6, and ASAS PR response using Flare Baseline as reference

---

- BASDAI50 response using Flare Baseline as reference
- SF-36 PCS response and SF-36 MCS response using Flare Baseline as a reference

## **Change #5**

### 2.2.2.2 Immunogenicity variables

The number and percentage of subjects with anti-CZP Ab levels above 2.4 units/mL will be reported as follows:

- Number and % of subjects with Ab >2.4 units/mL at the time of each visit
- Number and % of subjects with Ab >2.4 units/mL at any visit during treatment (not including the safety follow-up (SFU) visit)
- Number and % of subjects with Ab >2.4 units/mL at any visit including the SFU visit

For the subgroup of subjects with at least 1 anti-CZP Ab >2.4 units/mL, the time point of occurrence of the first finding will also be displayed.

## **Has been changed to:**

Anti-CZP antibody (ADAb) levels will be assessed at Baseline and subsequent time points as described in the protocol.

Determination of ADAb will be done using a validated screening, confirmation, and titration ADAbr bridging assay, with potential further characterization by a neutralizing antibody (NAb) assay. The immunogenicity data will be processed according to dedicated Bioanalytical Analysis plans.

## **Change #6**

### 3.2.4 MRI assessments

MRI will be assessed centrally and scoring will be done by 2 independent readers, who are blinded to both the order of the scans and to the treatment group, using a previously reported scoring system. Two different MRI scores will be used for analysis.

## **Has been changed to:**

Magnetic resonance imaging of the spine and sacroiliac joints will be performed at Screening, Week 48, Week 96, or WD Visit if MRI was performed more than 12 weeks prior to WD. MRI will be assessed centrally and scoring will be done by 2 independent readers, who are blinded to both the order of the scans and to the treatment group, using a previously reported scoring system. In addition, a single reader assessment will be performed for change from Baseline (Week 48) evaluation in the MRI scores for all subjects that entered Part A. Two different MRI scores will be used for analysis.

## **Change #7**

### 3.2.7 Ankylosing Spondylitis Disease Activity Score (ASDAS)

$0.579 \times (\text{natural logarithm of the CRP [mg/L]} + 1)$

## **Has been changed to:**

---

$0.579 \times (\text{natural logarithm of the (CRP [mg/L] + 1)})$

### **Change #8**

3.2.7 Ankylosing Spondylitis Disease Activity Score (ASDAS)

- ASDAS-MI: ASDAS reduction (improvement) of  $\geq 2.0$  relative to Baseline.

### **Has been changed to:**

- ASDAS-MI: ASDAS reduction (improvement) of  $\geq 2.0$  relative to Baseline. As a sensitivity analysis, ASDAS-MI analyses will be repeated using a Modified ASDAS-MI: ASDAS reduction (improvement) of  $>= 2.0$  relative to Baseline or has the lowest score possible post-baseline (i.e. when  $\text{CRP} < \text{LLOQ}$  and all other components are 0, then the minimum ASDAS score is 0.636 to 3 decimal places).

### **Change #9**

3.2.22 Flare

The following part has been added:

(in case of an unscheduled ASDAS visit at Week 94).

### **Change #10**

3.2.22 Flare

The following part has been added:

There is also the possibility to report one unscheduled ASDAS between two scheduled ASDAS assessments. The same rules as for the scheduled ASDAS apply for the unscheduled ASDAS.

The unscheduled ASDAS will be taken into account for flare calculation for two consecutive visits if there are more than 13 calendar days between two consecutive ASDAS calculated dates.

If the ASDAS score is missing at 2 scheduled visits and unscheduled ASDAS entry present in between and not larger than 3.5, then the subject will not be considered to have experienced a flare.

